## Statistical Design Plan

The data analysis plan is a series of steps including data entry, data cleaning, exploratory data analysis, and multivariate analysis, led by our biostatistician ([name]) and by our economist ([name]) for the economic analysis. Data will be managed at JHU and the data manager will review data for quality. Qualitative data will be de-identified, transcribed and translated (if needed) by research assistants, kept on password protected computers, and analyzed using Atlas-ti 8.4. Quantitative data will be de-identified, entered into Microsoft Access databases and analyzed using Stata 14. These data will be collected through direct observation (e.g., availability), electronic point of sale data collection (e.g., sales), surveys (e.g., consumer purchasing), and anthropometry (e.g., BMI). We will look at the change in availability, sales, and purchasing of healthier foods scores from baseline to post-intervention comparing intervention and comparison groups, at the store and consumer levels. Models will control for covariates that predict the outcomes (e.g., store size or consumer age and sex), and standard errors will account for the clustering of repeated measures within stores.

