### **C. APPROACH**

#### **C.1. Overview and study design**

The overall goal of this R34 application is to develop a stable mobile application to improve access to healthier foods and beverages in small corner corners in low-income urban settings, and to generate preliminary

findings in support of a full-scale clinical trial. The first part of the study will focus on developing a working, mobile accessible version of the BUD app. The second part will employ a randomized controlled trial study design where we will test the app, introduce different features to address identified challenges, and assess feasibility and impact primarily at the store level. Thirty-eight small corner stores located in East Baltimore will be randomized into treatment (n=19 receiving the BUD app) or comparison (n=19). The study will be conducted in seven overlapping phases, over a 33-month period:

Phase 1: Formative research (months 1-5)

Phase 2: BUD app development (months 3-8)

Phase 3: BUD function and usability testing (months 7-12)

Phase 4: Recruitment and baseline data collection (months 10-12)

Phase 5: Randomization, BUD pilot app implementation, process evaluation (months 13-20)

Phase 6: Post intervention data collection (months 21-23)

Phase 7: Data analysis and reporting (months 24-33)

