### Analysis of pilot trial store impact data (Aim 3)

We hypothesize that there will be significantly increased availability (stocking) and sales of healthy promoted foods (whole grain, fruit, vegetable, and low-fat, low-sugar foods) and beverages in intervention stores using the BUD app, as compared to comparison stores. Using direct observation-based stocking data, a healthy food availability index (HFAI) will be calculated, and we will initially examine the difference from pre- to

postintervention comparing intervention and control stores. We will also look at change in availability and sales of specific promoted product categories from pre- to post-intervention at each specific phase of intervention. Mixed-effect models, treating the stores as a random effect, will be used to evaluate the effect of the intervention on availability/sales of healthful food and beverage scores comparing corner store intervention and comparison groups, adjusting for covariates, such as store size and food stocking at baseline. We hypothesize that prices of some promoted foods and beverages will decrease given promoted foods/beverages will be subsidized during the first two phases of the intervention, as compared to baseline (if stocked at baseline). Furthermore, we will conduct additional tests to see if a pass-through price effect occurred related to the initial subsidy. Since the subsidy is short term (just phases 1 and 2 of the intervention), relatively small, and intended to generate initial usage of the app, we do not anticipate a significant price effect.

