#### **Power Calculation and Study Design**

This is a randomized group-treatment trial, where individual stores will be randomized to two study conditions: 1) usage of a web-based app (BUD) to order healthier food and beverages + in-store point-of-purchase promotional materials + limited subsidies (treatment); or 2) only in-store point-of-purchase promotional materials (comparison). In order to ensure a balanced study design, prior to randomization, we will stratify corner stores by two factors to balance potential confounders: 1) length of time in business at this location (>2 years vs <2 years); and 2) store size (0-2 aisles vs 2-4 aisles), and then randomize matched pairs to treatment versus comparison.

We recognize that clustering may occur, given that storeowners will share a change agent (BUD app) with other storeowners assigned to intervention group, and will potentially interact with each other as part of the functioning of the BUD app. We will control for baseline covariates of all participating stores that may predict study outcomes.

The feasibility pilot study is powered based on seeing impact at the corner store level. Store eligibility criteria for participation in the trial are as follows: 1) store owner/manager willing to order food through a smartphone or other internet-enabled device; 2) store located in a low-income neighborhood classified as a healthy food priority area in East Baltimore; 3) classified as small food store (< 4 aisles, < 2 cashier); 4) English, Korean, Spanish or Mandarin-speaking; and 5) located >0.25 miles from a supermarket.

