Sample size calculations for corner stores were based on the analysis of a simple difference in change in the mean of Healthy Food Availability Index (HFAI) scores. We used preliminary impact data from our previous trial (BHCK), with a reported mean change in HFAI  $\mu(\sigma) = 1.67(5.35)$  and  $\mu(\sigma) = 5.65(4.95)$  in the control and intervention groups, respectively. Due to the price incentive features (subsidy, group purchasing discounts) that will be available to BUD stores owners to stock healthier foods and beverages in phases 1 and 2, we estimate that the effect of the BUD intervention will be higher than our previous studies with corner stores. Therefore, we estimated a total sample size of 34 stores (17 per arm) for two-sample comparison of mean assuming a difference in healthy food availability (HFAI) of 6 points, variance of 24, intraclass correlation of 0.0001, type I error of 5% and power level set at 80%. We will increase our store sample size by 2 per treatment arm (n=38) to account for possible loss to follow-up. As mentioned, we will also control for baseline covariance, which will help to increase the power of the study. Some of the potential factors to control for will include store size and baseline HFAI.

The consumer sample size of this feasibility trial is intended to obtain an estimate of effect size and the variance in food consumption, purchasing, and body mass index, in order to plan a larger clinical trial, and to provide evidence of recruitment and retention ability. Therefore, the R34 pilot study is not powered to provide impact at the consumer level (which will be the primary outcomes for the full-scale clinical trial). Consumer eligibility criteria are as follows: 1) frequent consumer of the food store (shop at least once a week); 2) live/work within 1/4 mile radius from the store; 3) >21 years old and < 75 years old; 4) live in a household of at least 2 persons. We will use systematic sampling to recruit the consumer study evaluation sample in and around each of the 38 small food stores (5 adult consumers per food store).

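### The powered store-level comparison rests on 38 stores, but no small-sample inference method is named; with large-sample tests the stated 5% type I error would be roughly 5-8%, depending on the model.

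*Combined protocol and SAP*

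**What the plan says.** Section C.1 allocates 38 stores, 19 to each arm. The Power Calculation and Study Design section states that the pilot is powered at store level. It plans "a total sample size of 34 stores (17 per arm) for two-sample comparison of mean", with "type I error of 5% and power level set at 80" per cent, and then adds stores: "We will increase our store sample size by 2 per treatment arm (n=38) to account for possible loss to follow-up". Stores are stratified by time in business and by store size, and the plan will then "randomize matched pairs to treatment versus comparison".

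For analysis, the opening of the Statistical Design Plan says that "standard errors will account for the clustering of repeated measures within stores". The Aim 3 section specifies "Mixed-effect models, treating the stores as a random effect", adjusted for an open list of covariates of which two are named: store size and baseline stocking. Aim 3 also states a hypothesis of significant increases in availability and sales.

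Section C.11 refers the reader to the Statistical Design Plan for analysis details. That plan does not say whether models are fitted by maximum likelihood (ML) or restricted maximum likelihood (REML), whether tests use a normal or a t/F reference, how degrees of freedom are found, or whether the robust standard error is corrected for few stores. It does not say how the pairs enter the analysis. It names Stata 14, but that does not settle these choices.

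**The concern.** Mixed models and cluster-robust standard errors can both be used with large-sample or small-sample inference, and with 38 independent units the choice is visible. ML divides by the number of stores rather than by the residual degrees of freedom, so its variance is too small. The normal critical value of 1.96 is below the t value that applies. The two errors act in the same direction. If both are present, confidence intervals on the one comparison that the trial is powered for are too narrow, and the test does not have the 5% size that the plan states. The pilot is also meant to supply variance and clustering estimates for the main trial, so the estimator matters beyond the p-value.

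**Working it through.** **Inputs from the documents.** 38 stores, 34 after the planned loss; 5% type I error; two named covariates; stocking observed at five time points (C.8.3); matched-pair randomisation. **Assumptions.** Two-sided test (sidedness is not stated); normally distributed outcomes; 4 to 6 fixed effects in the ANCOVA cases.

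**The plan's own sample size.** The inputs are given as "assuming a difference in healthy food availability (HFAI) of 6 points, variance of 24, intraclass correlation of 0.0001". The normal formula gives 2 × (1.96 + 0.8416)² × 24 / 6² = 10.5, so 11 per arm (12 with a t-based formula), not 17. The stated 34 stores therefore do not follow from the stated inputs. That is a separate matter. The size of the test depends only on the number of stores, the model and the reference distribution.

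**Size when |estimate/SE| is compared with 1.96.** T_df denotes a t variable on df degrees of freedom.

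- Unbiased variance: size = P(|T_df| > 1.96).
- ML variance: size = P(|T_df| > 1.96 × √(df/n)), because ML divides the residual sum of squares by n instead of df.

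| Analysis | 38 stores | 34 stores |
|---|---|---|
| Two-sample t test on change scores, t reference | 5.0% | 5.0% |
| Random intercept, five visits, covariance correct (df = 4n − 2 = 150 or 134), z; unbiased to ML | 5.2-5.3% | 5.2-5.4% |
| Difference in change, unbiased variance, z (df 36 or 32) | 5.8% | 5.9% |
| Pre/post arm-by-time contrast, ML, z (df 36 or 32) | 6.4% | 6.6% |
| Store-level ANCOVA, ML, z, 4 fixed effects (df 34 or 30) | 7.2% | 7.6% |
| As above, 5 fixed effects | 7.7% | 8.1% |
| As above, 6 fixed effects | 8.2% | 8.6% |

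For ANCOVA with 38 stores, the effective cut-off is 1.96 × √(34/38) = 1.854, and P(|T_34| > 1.854) = 7.2%. The four fixed effects are intercept, arm, store size and baseline stocking. In the pre/post arm-by-time model, covariates that do not vary over time use no degrees of freedom of the change contrast. The cut-off is 1.96 × √(36/38) = 1.908 however many are added, which gives 6.4%.

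**Interval width, 38 stores.** With an unbiased variance and z, the correct interval is 2.028/1.96 = 1.035 times as wide. With ML ANCOVA and four fixed effects it is (2.032/1.96) × √(38/34) = 1.10 times as wide.

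**Cluster-robust standard errors (simulation).** An uncorrected sandwich with z gave 6.2-6.7% for difference-in-differences (38 or 34 stores). For store-level ANCOVA with 38 stores it gave 6.3-8.5%, and up to 9.3% with 34 stores and four covariates. In difference-in-differences, a finite-cluster factor and a t reference on stores minus 1 gave 4.3-5.0%. Store-level ANCOVA with an unbiased variance and a t reference gave 4.9-5.2%.

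**Effect of the matched pairs.** Suppose outcomes have residual correlation ρ within pairs and the pairs are left out. The true variance of the arm difference is then smaller by the factor 1 − ρ, so the effective cut-off rises to about 1.96/√(1 − ρ), or 1.908/√(1 − ρ) with ML. On 36 df:

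- ρ = 0.05: about 5.2% (ML 5.8%).
- ρ = 0.10: about 4.6% (ML 5.2%).

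A simulation agreed to within about 0.1 percentage points. In a further ANCOVA simulation, the ML/z size fell from 7.5% to 4.7% as an unadjusted matching factor became strongly prognostic. If instead the pairs are analysed as pairs but z is kept, the size is 6.6% (unbiased) to 7.3% (ML) with 19 pairs, and 6.8-7.5% with 17.

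**The case against.** The strongest reply is that this is an unspecified detail and not a stated wrong method. That stands. The documents never mention ML, z tests or an uncorrected sandwich, and REML with a t reference would satisfy every sentence quoted. The sample-size text describes a two-sample comparison of mean change, and Aim 3 begins with a simple pre-to-post difference between arms. A t test on those 38 changes has exactly 5% size under normality. However, the sample-size text is a planning calculation, and the analysis that Aim 3 goes on to specify is the adjusted mixed model.

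A reader might infer that the trial will run at 6-8%. The documents do not support that. The figures above 7% need both ML and z in a store-level ANCOVA (or, with the pairs modelled, in a paired analysis), or an uncorrected sandwich. Only two covariates are named, so the cases with five or six fixed effects are assumptions. Omitting the pairs also works in the opposite direction. The offset is uncertain, because adjusting for store size may already absorb part of the within-pair correlation.

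It is also fair to say that this is a pilot and that the documents tie no go/no-go rule to p < 0.05. That limits the consequence. It does not remove the point, since the plan states a 5% error rate and a significance hypothesis for this comparison.

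**Conclusion.** The point holds in conditional form. The plan names no small-sample method for a comparison of 38 stores, so it permits analyses that miss its own 5%. Under large-sample inference the size is roughly 5-8%: close to nominal for a correct five-visit random-intercept model, 5.8% with an unbiased variance, 6.4% for ML on the pre/post contrast, and 7.2% for ML ANCOVA with the named covariates. It is higher with further covariates or store loss. Unmodelled pairing could cancel some or all of the excess. These figures assume two-sided tests and normal outcomes; all but the pairing calculations also assume independent stores. Severity is minor.

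**What to change.** Add to the Aim 3 section, before analysis:

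1. Fit the store models by REML, with Kenward-Roger or Satterthwaite degrees of freedom for the arm effect.
2. Where a cluster-robust standard error is used, use a bias-reduced version with a t reference on store-based degrees of freedom.
3. Reflect the randomisation: include the matched pairs, or at least both stratification factors (time in business and store size), with degrees of freedom to match.

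Item 3 is needed alongside items 1 and 2. A t test on 36 df that ignored a within-pair correlation of 0.10 would have a size of about 3.9% (cut-off 2.028/√0.90 = 2.138).

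The cost is a few sentences and no new data. Intervals widen by about 3.5% relative to z with an unbiased variance, or about 10% relative to ML with z and four fixed effects. Adding time in business to the two named covariates uses one more degree of freedom (34 to 33). Full pair effects leave 18 degrees of freedom with 19 pairs and no other covariates, so the t cut-off is 2.10 instead of 2.03. The choice should be made in advance.

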### Feasibility analysis (Aims 1 and 2)

In-depth interviews will be analyzed in ATLAS.ti for themes, and used to inform changes to the BUD app and to assess feasibility from the perspective of users. Feasibility analysis will focus on assessing economic and cultural acceptability, operability and perceived/planned sustained use of the BUD app, including barriers and enhancing factors. From the corner store owner/wholesaler/producer perspectives, acceptability will be assessed according to whether the new products are perceived to be in demand, profitable, easy to obtain and store. Operability will be assessed primarily in terms of the BUD app, in terms of whether store owners indicate (and demonstrate) that they can and do continue to use the different features of the app (e.g., BuddyUp, BuddyLift, Buddy Chat, etc.). Perceived sustainability will be assessed in terms of whether store owners (and other users, such as wholesalers, producers) indicate that they plan to continue to use the BUD app, how much, and for what purposes (e.g., which specific foods). Textual data will be coded by trained staff using a codebook. The codebook will emphasize these feasibility constructs. Qualitative analysis will center on providing contextually rich descriptions of each aspect of feasibility, and describing some of the key sources of variation (e.g., by store size, owner ethnicity, etc.). Analysis of the 20 qualitative consumer interviews will focus on identifying those healthier products would be most acceptable to them in terms of demand, cost, taste and other similar characteristics. The analysis will also identify best in-store strategies to promote these foods.

We will conduct a detailed quantitative process evaluation (in terms of reach, dose delivered, and fidelity), and results will serve as additional measures of feasibility, particularly in terms of establishing operability and potential sustainability. Three primary process dimensions will be assessed: reach, dose delivered and fidelity – each will likely have multiple measures – and standards will be set for each measure to monitor quality of intervention implementation. For example, reach will be assessed by the percent of intervention corner stores ever using the BUD App for ordering, and the number of wholesalers/producers who ever put products on the app. The standard could be set at 100%, meaning that each corner stores/wholesaler/producer used the app at least one. Dose delivered will be evaluated as the percent of BUD app trainings successfully completed by corner store owners (out of 18 possible intervention stores) – currently planned at one/phase of the intervention (n=4), # communications with store owners (out of X possible communications, determined by a standard to be set), and delivery of promotional materials to encourage consumer demand (out of X possible deliveries, determined by a standard to be set). Fidelity will be assessed as frequency of usage (e.g., once per week, twice per week) of the BUD App to offer/order foods and beverages by wholesalers/producers/corner store owners, as well as in terms of their use of different features of the app (e.g., BuddyUp, BuddyLift, BuddyChat, etc.). We will set standards to monitor quality of intervention implementation for the reach, dose and fidelity measures, and revise these standards based on the experience of the R34 trial for the planned future full-scale trial.

Feasibility will also be assessed via analysis of user satisfaction responses collected during operation of the BUD app, as well as in terms of responses to the open-ended questions that will be part of the process evaluation measures.

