### **C.9. BUD Pilot App Implementation (Phase 5)**

We will pilot the BUD app in 19 intervention corner stores over an 8-month period in East Baltimore. We will select stores only located in East Baltimore for logistical ease, and to keep delivery costs lower. The pilot will be conducted in four stages (2 months each), differentiated by the types of foods and beverages promoted, BUD features activated, and limited subsidy (BUD Credit) provided. During the first weeks of each stage, training of participating corner store owners and producers/wholesalers will take place – focusing on use of the BUD app and any new features, specific foods/beverages and guidance for promotion. Initial training will be followed up by proficiency testing where intervention store owners will be requested to complete certain functions (e.g., enroll in a BuddyUp! deal, fill out a user satisfaction form, etc.). With each subsequent stage, more app features will be made available to users (Table 1). During stage one, the basic BUD app interface will be introduced to corner store owners and low-sugar beverages will be promoted. In stage two, in addition to the basic BUD app interface, the BuddyUp! feature will be introduced to store owners, and fresh fruits and vegetables will be promoted. In stage 3, the BuddyLift! feature will be activated, and low-fat whole grains. Stage four will focus on reinforcement. On the BUD app, promoted items will be highlighted on the homepage (e.g., *Great Deal! Only 1 more buyer needed to get strawberries delivered for just \$3/pound! Click here for more information*).

*Bundled subsidy: To generate initial engagement and use of the app, we will bundle the app with initial limited subsidies (BUD Credit), which reflects common promotional practices for the introduction of new apps. A subsidy (\$100/stage) will be offered for stages 1 and 2 only. The subsidy will only be usable for the products being promoted during that stage. Small store owners will only be able to spend \$50/week maximum in order to encourage multiple orders, building familiarity with BUD's functions. BUD Credit will be usable to pay all or part of any transaction (for example, a corner store owner could use \$5 to cover part of the delivery costs of \$25 worth of strawberries, or \$30 to cover the entire cost).*

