### **C.10. Post-intervention Data Collection/Feasibility Assessment (Phase 6)**

*All phase 4 data collection instruments (wholesaler, producer, food store, consumer) will be repeated in Phase 6 to assess change associated with the BUD intervention. We will also conduct in-depth interviews with our 19 intervention corner store owners and participating wholesalers/producers to understand feasibility of the BUD app. This will include questions on acceptability (economic, cultural), operability (challenges, ease in using the app and its functions), and whether they would continue to use the app (perceived sustainability). In addition, we will conduct a follow-up study in 20 small stores in West Baltimore, Philadelphia and Detroit, where we demonstrate the BUD app, and assess feasibility through in-depth interviews. Additional description of feasibility constructs is provided in the Statistical Design Plan.*

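### The training-completion percentage is defined on 18 intervention stores, but the design has 19; counting all 19 over 18 overstates this one process measure by up to 5.6 percentage points

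*Combined protocol and SAP*

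**What the plan says.** Under Feasibility analysis (Aims 1 and 2), the Statistical Design Plan describes a quantitative process evaluation of reach, dose delivered and fidelity. One component of dose delivered is the percentage of BUD app "trainings successfully completed by corner store owners (out of 18 possible intervention stores"). The number of trainings is "currently planned at one/phase of the intervention (n=4").

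The other counts of the intervention arm are:

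- C.1, Overview and study design: the 38 stores are "randomized into treatment (n=19 receiving the BUD app) or comparison (n=19").
- C.9, BUD Pilot App Implementation: "We will pilot the BUD app in 19 intervention corner stores over an 8-month period in East Baltimore".
- C.10, Post-intervention Data Collection: the plan includes "in-depth interviews with our 19 intervention corner store owners".
- Power Calculation and Study Design: "we estimated a total sample size of 34 stores (17 per arm"), followed by "We will increase our store sample size by 2 per treatment arm (n=38").

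The feasibility section says that a standard will be fixed for each process measure. The only level it mentions is an example for reach: "The standard could be set at 100" per cent. It gives none for dose delivered.

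**The concern.** A completion percentage should be taken over the units that could have received the training. The wording refers to possible stores, so 18 cannot be read as an expected number of completers or retained stores; it purports to be the whole intervention arm. That arm has 19 stores.

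The number is also specific enough to be used. For the other two dose components in the same sentence (communications and promotional deliveries) the plan leaves the denominator as an unspecified X. For trainings it gives a figure, which an analyst could enter as it stands.

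At stake is a correct reading of how completely the training was delivered. The less visible error is the more troublesome one: a result of 100% could hide a store that completed no training at all.

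**Working it through.** **Inputs.** 17 stores per arm before allowance, 2 added per arm, 38 in total (Power Calculation and Study Design); 19 per arm (C.1); four trainings per store and a denominator of 18 stores (Feasibility analysis).

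**Step 1: can 18 be reproduced?**

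- Arm size from the power section: 17 + 2 = 19.
- Arm size from the total: 38 / 2 = 19.
- Arm size before the allowance: 34 / 2 = 17.
- Arm size if the whole loss allowance is used up: 19 - 2 = 17.

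The figure 19 is reproduced two ways and agrees with C.1, C.9 and C.10. None of these routes gives 18, and no section excludes a store from training or from the process evaluation.

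**Step 2: denominators in store-trainings.**

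- As written: 18 x 4 = 72.
- By design: 19 x 4 = 76.

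**Step 3: size of the error if all 19 stores are in the numerator.** With k trainings completed, the ratio of the two percentages is (k/72) / (k/76) = 76/72 = 19/18 = 1.056, whatever k is. The difference is k/72 - k/76 = 4k / (72 x 76) = k/1368, which is largest at k = 76.

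| Trainings completed | Over 72 | Over 76 | Difference (points) |
|---|---|---|---|
| 76 (all 19 stores, all four) | 105.6% | 100% | 5.6 |
| 72 (18 stores, all four) | 100% | 94.7% | 5.3 |
| 68 (17 stores, all four) | 94.4% | 89.5% | 5.0 |

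Reporting each training round separately gives the same ratio, since it compares m/18 with m/19.

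**Step 4: if the numerator is also limited to 18 stores.** The percentage then cannot exceed 100%, but it depends on which store is left out. Take 68 completed trainings in all, a true 89.5%. If the omitted store completed none, the result is 68/72 = 94.4%. If it completed all four, the result is (68 - 4)/72 = 64/72 = 88.9%. The plan names no store to omit and gives no reason for omitting one.

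**The case against.** The best case for leaving this alone is that it is an evident slip in provisional text. The number of trainings is only the current plan, the sibling denominators are still open, and the standards are yet to be set. A result of 105.6% would expose itself at once. The counts elsewhere are not perfectly tidy either: the Economic analysis (Aim 5) uses 170 consumers, which at five per store is 34 stores, against the 190 (38 x 5) in B.5 and C.8. The 18 may likewise be a count that was not updated, though the documents do not say so.

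Most of this stands, and it limits the weight of the point. It does not remove it: a reported 100% with one store missed would not expose itself, and an unreconciled count elsewhere is no ground for assuming that this one will be put right.

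Three stronger readings are tempting, and the documents do not support them:

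- *That the error carries a result across an implementation threshold.* No standard for dose delivered exists. The 100% example is for reach, and any other cut-off would be the reader's own.
- *That the feasibility findings as a whole are inflated.* Only training completion uses the 18. Reach is a percentage of intervention stores with no number attached, and fidelity is frequency of use. The plan treats process results as additional to its interview-based assessment of feasibility. It does intend to revise process standards for the full trial from this experience, but states no go/no-go rule on this measure. Its section on powering the main trial relies on outcome changes, correlations and the ICC.
- *That the percentage will necessarily be overstated.* Step 4 shows that this depends on how the numerator is counted.

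**Conclusion.** The denominator of 18 is wrong as written: four places in the same document give 19 and none explains 18. The consequence is minor. If trainings from all 19 stores are counted, the training-completion percentage is too high by a factor of 19/18, at most 5.6 percentage points, and can reach 105.6%. If the numerator is restricted to 18 stores, one randomised store disappears and the direction of the error depends on that store.

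The sizes assume four trainings per store, as currently planned, and 19 stores actually randomised to the app. The Aim 3 comparison and the sample size are unaffected.

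**What to change.** In the Feasibility analysis (Aims 1 and 2), replace 18 with 19 randomised intervention stores and state the resulting total: 76 store-trainings at four per store. Should the number of trainings change, the total becomes 19 times the new number.

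The cost is one number and a short clause. Design, data collection and the other analyses do not change; the reported percentage will be slightly lower than it would be over 72. The 170 versus 190 consumer count can be reconciled in the same edit. How to treat stores that close or stop using the app is a separate choice, which this mismatch does not settle.
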